3.3 Exit DBPCFC

All subjects who reach the targeted daily dose of 300 mg and maintain that dose through the Maintenance Period will undergo an Exit DBPCFC. The Exit DBPCFC will be performed in accordance with PRACTALL guidelines, but starting at a dose of 3 mg of peanut protein (except for subjects who reacted to 1 mg in their Screening DBPCFC; these subjects will be required to start their Exit challenge at 1 mg; [Section 6.6.2](#)) and requiring progression in a fixed sequence ([Table 3](#)), without repeating any dose. Also, the Exit DBPCFC will include a 600 mg challenge dose, and the top challenge dose will be capped at 1000 mg.

The same vehicle food should be used for the Exit DBPCFC as was used for the Screening DBPCFC.

For each subject, a Blinded Evaluating Physician (Blinded Assessor) is to be designated to assess the tolerability of the challenge doses presented in the DBPCFC. The Blinded Evaluating Physician, who is assessing and managing subject symptoms on the food challenge days, is not to be involved directly in the oversight of study product dosing or the assessment or management of AEs during the initial escalation, up-dosing, or maintenance phases of the study; nor should he or she be involved in the food challenge material preparation on the food challenge days. To the extent practicable, the same Blinded Evaluating Physician who determines DLS in the Screening DBPCFC should determine DLS in the Exit DBPCFC.

Each subject will be unblinded after he/she completes the DBPCFC, all major data queries to date (ie, queries that could influence allocation to 1 or another analysis population) for the subject have been resolved, and the follow-on study ARC008 is available at the study site. Subjects may continue blinded study treatment and have clinic visits every 4 weeks in ARC010 until ARC008 is available, unless specified otherwise ([Section 3.4](#)). To maintain the study blind overall, individual unblinding information should only be distributed to designated team members on a need-to-know basis as instructed by Aimmune.

Subjects who do not reach the target dose of 300 mg/d by Week 40 are not eligible for the Exit DBPCFC. These subjects will be unblinded once the database has been locked and unblinded.

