3.7 Primary Efficacy Endpoint

The primary clinical efficacy endpoint is the proportion of subjects who tolerate at least 1000 mg as a single dose (2043 mg cumulative) of peanut protein with no more than mild symptoms at the Exit DBPCFC.

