on any study day. Blood draw should be collected in compliance with local laboratory guidelines and testing regulations. Multiple attempts to obtain blood, and repeat samples can be collected where necessary for damaged samples or safety reasons.

- SPT to peanut extract
- Monitoring for AEs, including allergic symptoms ([Section 6.7](#) and [Section 7.2](#))

In addition to the procedures listed above, eligible subjects will have an Exit DBPCFC performed. Eligible subjects are those who tolerate 300 mg/d and are maintained at this dose for the approximately 12-week Maintenance Period. Subjects may have a dose reduction but must be on a dose of 300 mg/d without symptomatic therapy for the 4 weeks immediately preceding the Exit DBPCFC. The Exit DBPCFC is to be conducted in accordance with PRACTALL guidelines, with the protocol-specified modifications, as described in [Section 6.6.2](#).

Each subject participating in the study will be unblinded when he/she completes the Exit Visit procedures (including the Exit DBPCFC for eligible subjects), all major data queries (ie, queries that could influence allocation to 1 or another analysis population) for the subject have been resolved, and the follow-on study ARC008 is available at the study site (refer to [Section 3.3](#)). If the open-label follow-on study ARC008 is not yet available at the study site, the subject may continue blinded study treatment and have clinic visits every 4 weeks in ARC010 until ARC008 is available. Subjects who complete 12 weeks of maintenance and who do not tolerate 300 mg peanut protein at the Exit DBPCFC will not continue blinded study treatment in ARC010.

All AR101-treated subjects who pass the Exit DBPCFC at the 443 mg cumulative dose level of peanut protein (ie, tolerate 443 mg cumulative dose with no more than mild symptoms) are eligible to proceed to ARC008. All placebo-treated subjects who complete the study are eligible for rollover into ARC008.

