6.12 Study Blinding Procedures

This is a double-blind study. The study as a whole will not be unblinded until after the last subject exits ARC010 and the database is locked.

After undergoing the Exit DBPCFC, most subjects will, however, become de facto unblinded to their on-study treatment assignment on the basis of their experience with the food challenge (ie, subjects who fail 1 part of the Exit DBPCFC early on may reasonably deduce that they had been in the placebo arm of the study), and those who tolerate both parts of the Exit DBPCFC (or fail 1 part only at the highest dose levels tested) may reasonably deduce that they had been in the AR101 arm. Hence, the study is double-blinded on an individual subject basis only up to completion of the Exit DBPCFC. It is for this reason that assessment of reactions to DBPCFC will be made by a Blinded Evaluating Physician (Blinded Assessor).

The risk of bias being introduced into the determination of DLS during DBPCFCs will be substantially reduced by having the assessment of the DBPCFC results made by a Blinded Evaluating Physician (Blinded Assessor) who is not otherwise directly involved, during the treatment phase, with the treatment of the subjects he or she is evaluating.

Additionally, to ensure that allocation of subjects to their appropriate analysis populations is not biased by knowledge of their treatment assignments, specific masking procedures have been put in place to shield study team members who could be involved in determining allocation of the subjects to the analysis populations from knowing subject treatment assignments (refer to Masking Plan). To further ensure that allocation of subjects to their appropriate analysis populations is performed in an unbiased way, subjects will not be informed of their on-study treatment assignments or rollover into the open-label follow-on study until all major data queries (ie, queries that could influence allocation to 1 or another analysis population) have been resolved (as detailed in the Masking Plan).

Subjects who discontinue the study prior to the Exit DBPCFC are not unblinded until after database lock and unblinding of the study as a whole.

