9.1 Analysis Populations

The ITT population (ie, the Full Analysis Set) will consist of all randomized subjects who received at least 1 dose of randomized study treatment (AR101 or placebo). Subjects will be analyzed according to randomized treatment. The ITT population will be used as the primary analysis population for all analyses of efficacy endpoints.

Since only a small number of subjects are expected to be randomized but not treated and due to the double-blind nature of the trial, no bias is introduced by excluding these subjects from the ITT population. In order to verify this expectation, sensitivity analyses will be performed using the randomized population for the primary and key secondary endpoints.

The Completer population will include all subjects in the ITT population who undergo the Exit DBPCFC.

A Per Protocol (PP) population may be defined for this study. The PP population will be a subset of the Completer population, limited to subjects who have no major protocol deviations that may influence the desensitization response. Exclusions will be determined by blinded review before database lock and overall study unblinding. Subjects will be analyzed according to randomized treatment.

Sensitivity analyses, to be described in full in the SAP, will be performed using the Completer population and PP population (the latter if sufficiently different from the Completer population).

The Safety population will consist of all subjects who receive randomized study treatment. The Safety population will be used for summaries of safety parameters. Subjects will be analyzed according to treatment received.

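### Individual unblinding waits only for queries that bear on analysis-population allocation, so queries on the Exit challenge outcome may still be open once the arm is known

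*Protocol*

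**What the plan says.** Sections 3.3 and 6.5 and the synopsis set three conditions for unblinding an Exit DBPCFC subject: the challenge (in 6.5, the Exit Visit procedures) is complete, the major data queries are resolved, and ARC008 is available at the site. Section 3.3 defines the queries as "all major data queries to date (ie, queries that could influence allocation to 1 or another analysis population"), and 6.5 repeats this: "all major data queries (ie, queries that could influence allocation to 1 or another analysis population"). Section 4.3.1 and Appendix 1 note bb reuse the term without redefining it.

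Section 6.12 withholds the assignment "until all major data queries (ie, queries that could influence allocation to 1 or another analysis population) have been resolved" and refers to the Masking Plan for details. It gives the purpose as: "To further ensure that allocation of subjects to their appropriate analysis populations is performed in an unbiased way". It also states: "Hence, the study is double-blinded on an individual subject basis only up to completion of the Exit DBPCFC". The study as a whole is unblinded only after the last subject exits and the database is locked.

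On the endpoint, 3.7 reads: "The primary clinical efficacy endpoint is the proportion of subjects who tolerate at least 1000 mg as a single dose (2043 mg cumulative") with symptoms no worse than mild. On the populations, 9.1 says: "The Completer population will include all subjects in the ITT population who undergo the Exit DBPCFC"; the Per Protocol set is a subset of it, "limited to subjects who have no major protocol deviations that may influence the desensitization response".

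**The concern.** The query condition protects the assignment of subjects to analysis sets. It does not name the data that decide whether a subject is a responder. Those data involve judgement. Under 6.6, mild symptoms may or may not be dose limiting, moderate symptoms may be excused with a documented explanation, and a challenge stopped without convincing dose-limiting symptoms needs an explanation in the CRF. Such entries attract queries.

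If a query of this kind is answered after the arm is known, the answer can be influenced by that knowledge. The primary endpoint, the three key secondary endpoints and the two MTD endpoints all draw on these pages. No section of the protocol requires the pages to be signed off, cleared of queries or frozen before the individual subject is unblinded.

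**Working it through.** The point is procedural, so the main check sets the sections side by side. The arithmetic only gives scale.

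**1. Does any population depend on the challenge outcome (9.1)?**
- ITT: randomised and at least one dose. No.
- Completer: underwent the Exit DBPCFC, whatever the result. No.
- Per Protocol: Completer without a relevant major deviation. Not on the outcome itself, though a query on washout, dose sequence or challenge conduct can reveal a deviation and so come under the condition.
- Safety: received study treatment. No.

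A query on dose-limiting symptoms, symptom grade or treatment given is therefore outside the definition unless it also raises a deviation.

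**2. How long can the gap before lock be?** The synopsis expects a study of about 18 months. Section 1.4 gives about 9 months of treatment, and screening takes about 1 month (28 days). A subject enrolled at the start could finish about 18 − (9 + 1) = 8 months before the last visit, and be unblinded then if ARC008 is open at the site.

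**3. Will site staff learn the arm?** Under 3.4, former placebo subjects start ARC008 at 0.5 mg and former AR101 subjects receive 300 mg/d. Staff who treat them there will know. The protocol does not say whether the same people answer Exit challenge queries.

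**4. Which outcomes can a late edit change?** Each challenge part stops at dose-limiting symptoms (6.6), doses follow a fixed sequence without repeats (3.3), and a subject without an Exit DBPCFC is a failure by rule (9.2.1).
- Primary (1000 mg): a subject stopped at 600 mg or below never received 1000 mg and cannot become a responder. Only subjects given 1000 mg can be re-scored, in either direction.
- 600 mg, 300 mg and MTD: exposure lies mainly at the dose where the challenge stopped, because giving the next dose largely settles the one before.
- Maximum symptom severity: the worst grade (0 to 3) at any dose. No later dose anchors it, and every challenged subject contributes one, so it is the most exposed. It is tested last of the three key secondary endpoints.

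**5. Scale of one changed outcome.** Inputs from 9.4: 120 AR101, 40 placebo, 15% placebo response, two-sided Fisher's exact test at 0.05.
- The plan's power figures reproduce. Exact enumeration gives 82.8% at 39% v 15% (stated: at least 80%) and 92.1% at 43% v 15% (stated: at least 90%). Nothing in this point changes them.
- One subject: 1/120 = 0.8 points in AR101; 1/40 = 2.5 points in placebo.
- With 6/40 (15%) placebo responders, 37/120 AR101 responders gives p = 0.064 and 38/120 gives p = 0.043. A single change alters significance only at that boundary.

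**6. What cannot be computed.** The documents give neither the share of Exit challenges with an outcome query open at unblinding nor the share of such queries that would change an outcome. No estimate of bias follows from them.

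**The case against.** The strongest reply has four parts.

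- **Existing safeguards.** A Blinded Assessor kept out of treatment oversight determines dose-limiting symptoms, and 3.3 restricts unblinding information to designated team members who need it. Section 6.12 refers to a Masking Plan, where sign-off and query closure would commonly be set out. This stands as a limit on the risk. It does not remove the gap: the assessor's separation is defined for the treatment phases and for challenge preparation, and nothing says the assessor stays blinded afterwards or answers later queries. Where 6.12 cites the Masking Plan for query resolution, it again names population queries only.
- **De facto unblinding.** Section 6.12 accepts that most subjects can infer their arm from the challenge, and 6.6 lets staff learn the challenge order after the second observation period. Delaying formal unblinding therefore gains less than it seems. It still gains something: an inference from the result only mirrors the result, while formal unblinding adds information where result and arm disagree, such as an AR101 subject stopped at a low dose.
- **Outcomes largely fixed by events.** This stands for the primary endpoint, and less so for symptom severity.
- **ARC008 eligibility.** The 443 mg result decides rollover for AR101 subjects, which gives sites a practical reason to settle it early. It is not a stated rule, and it does not cover the other doses or the symptom grades.

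A reader might infer that Exit data are wholly unprotected after unblinding, or that every efficacy endpoint will be biased. The documents support neither: they show silence in the protocol text, alongside partial safeguards and one unseen plan.

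**Conclusion.** The point holds as a cheap improvement. As written, the condition lets queries on Exit DBPCFC tolerability, symptom severity and treatment given stay open when a subject is unblinded, and be answered before lock by staff who may know the arm. The exposure is narrow for the primary endpoint (subjects given 1000 mg), lies mainly at the stopping dose for the 300 mg, 600 mg and MTD outcomes, and is widest for maximum symptom severity.

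A reader might go further and infer an inflated Type I error. An illustration can be built: with 15% response in both arms, recoding 1%, 2%, 5% or 10% of AR101 non-responders as responders takes Fisher's rejection rate from 3.7% to 3.7%, 4.0%, 6.6% or 17.0%. Those shares are assumed, the changes run in one direction only, and the pool includes dropouts and early-stopped subjects who cannot become responders. It does not measure this trial's risk. The conclusion rests on the protocol text alone and assumes that the Masking Plan does not already close the gap.

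**What to change.** - Widen the definition of major data queries in the synopsis, 3.3, 6.5 and 6.12, with 4.3.1 and Appendix 1 note bb following it, to include every query on the Exit DBPCFC: dose-by-dose tolerability, symptom severity, treatment given and exception explanations.
- Require the Blinded Assessor to sign those pages, and require the pages to be frozen, before the subject is unblinded.
- Align the Masking Plan, or cross-refer to it if it already says this.
- List any later change to those pages by arm, with its reason, in the study report. This remains possible even for subjects already unblinded.

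The cost is a short amendment and possibly a few days' delay to some subjects' unblinding and rollover into ARC008. Sample size, alpha and power are unchanged.

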3.4 Open-label Follow-on Study – ARC008

All placebo-treated subjects who complete ARC010 are eligible for rollover into the open-label follow-on study ARC008. In ARC008, placebo-treated subjects from ARC010 will undergo an escalation schedule, starting with the 0.5 mg dose and proceeding sequentially through the Up-dosing and Maintenance Periods in an open-label fashion identical to that for subjects who received AR101 in the ARC010 study. If subjects tolerate a daily dose of 300 mg during the Up-dosing Period, they will enter the Initial Maintenance Period. Once 24 weeks in the Initial Maintenance Period have been completed, subjects will then enter the Extended Maintenance Period and receive 300 mg/d until the end of the study. Subjects will be offered optional annual food challenges.

All AR101-treated subjects in ARC010 who pass the DBPCFC at the 443 mg cumulative dose level of peanut protein (ie, tolerate 443 mg cumulative dose with no more than mild symptoms) are eligible to proceed to ARC008. Subjects will receive 300 mg a day for the duration of the study, with visits every 3 months to the CRC. They will be offered the optional annual food challenges. Subjects who do not pass the DBPCFC at the 443 mg cumulative challenge dose level will not be eligible to enroll in ARC008.

If ARC008 is not yet available at the study site, subjects may continue blinded study treatment and have clinic visits every 4 weeks in ARC010 until ARC008 is available. Subjects who do not tolerate 300 mg peanut protein at the Exit DBPCFC will not continue blinded study treatment in ARC010.

3.5 Definition of End of the Study

The end of the study is defined as the last visit of the last subject.

3.6 Study Design Safety Considerations

The study design incorporates the following important safety considerations:

- All dose escalations will be performed under direct observation and medical supervision in the CRC
- The peanut OIT will start at 0.5 mg and will only escalate to a maximum single dose of 6 mg during the initial escalation on Day 1
- AEs, including dosing-related allergic symptoms, whether expected or not, will be captured throughout the study
- All subjects and/or their participating family (as appropriate for age and home circumstances) will be provided with an epinephrine auto-injector and will be trained in its use
- Subjects will be strongly cautioned against consuming any peanuts or peanut-containing foods other than the IP while on study, and will be instructed to remain on a peanut-free diet

A DSMC will be established and will meet at time points defined in the DSMC charter to monitor the study for safety.

3.7 Primary Efficacy Endpoint

The primary clinical efficacy endpoint is the proportion of subjects who tolerate at least 1000 mg as a single dose (2043 mg cumulative) of peanut protein with no more than mild symptoms at the Exit DBPCFC.

3.8 Secondary Endpoints

3.8.1 Secondary Efficacy Endpoints

3.8.1.1 Key Secondary Efficacy Endpoints

The key secondary efficacy endpoints are as follows:

- The proportion of subjects who tolerate at least 600 mg as a single dose (1043 mg cumulative) of peanut protein with no more than mild symptoms at the Exit DBPCFC
- The proportion of subjects who tolerate at least 300 mg as a single dose (443 mg cumulative) of peanut protein with no more than mild symptoms at the Exit DBPCFC
- The maximum severity of symptoms occurring following ingestion of peanut protein during the Exit DBPCFC

3.8.1.2 Other Secondary Efficacy Endpoints

The other secondary efficacy endpoints are as follows:

- The MTD with no more than mild symptoms at Exit DBPCFC
- Change from baseline in MTD of peanut protein at Exit DBPCFC
- Use of epinephrine as a rescue medication at Exit DBPCFC and comparison to its use at Screening DBPCFC
- Changes in serum peanut- and peanut component-specific IgE, total IgE, and peanut-specific IgG4 levels
- Changes in peanut SPT mean wheal diameter
- Quality of life assessments using the food allergy quality of life questionnaire (FAQLQ) and the food allergy independent measure (FAIM; [van der Velde et al, 2010](#)) questionnaire

3.8.2 Exploratory Endpoints

- Treatment satisfaction assessment using the Treatment Satisfaction Questionnaire for Medication (the TSQM-9) and an exit questionnaire
- Assessment of palatability (taste and after-taste)

3.8.3 Safety Endpoints

- The safety of peanut OIT based on AEs and SAEs
- Use of epinephrine as a rescue medication during OIT (Initial Escalation, Up-dosing, and Maintenance Periods)
- Frequency and severity of anaphylaxis during OIT (Initial Escalation, Up-dosing, and Maintenance Periods), attributable to IP or accidental food exposure
- Frequency and severity of allergic reaction (hypersensitivity) AEs occurring during the Up-dosing versus the Maintenance Period, normalized for duration of treatment
- Frequency of accidental ingestion of peanut and other allergenic foods; frequency and severity of reactions resulting from accidental ingestion of peanut and other allergenic foods
- Frequency and severity of premature discontinuation of dosing due to AEs; and frequency of premature discontinuation of dosing due to chronic/recurrent GI AEs
- Assessment of asthma control using the 2007 National Heart, Lung, and Blood Institute (NHLBI) classification and the Asthma Control Test questionnaire in subjects with asthma

4. SELECTION AND WITHDRAWAL OF SUBJECTS

4.1 Inclusion Criteria

Subjects who meet all of the following criteria are eligible for enrollment as study subjects:

1. Age 4 through 17 years (inclusive)
2. Clinical history of allergy to peanuts or peanut-containing foods

3. Serum IgE to peanut of ≥ 0.35 kUA/L (as determined by UniCAP™ within the past 12 months) and/or a peanut SPT wheal diameter ≥ 3 mm compared to control
4. Experience DLS at or before the 300 mg (444 mg cumulative) challenge dose of peanut protein (measured as 600 mg of peanut flour) on Screening DBPCFC conducted in accordance with PRACTALL guidelines
5. Written informed consent from subjects or parent/guardian for all subjects (or both parents when required by local authorities)
6. Written assent from minor subjects as appropriate (in accordance with local regulatory requirements)
7. Use of effective birth control by female subjects of childbearing potential ([Section 7.10.3.2](#))

4.2 Exclusion Criteria

Subjects who meet any of these criteria are not eligible for enrollment as study subjects:

1. History of hemodynamically significant cardiovascular disease, including uncontrolled or inadequately controlled hypertension ([Section 5.10](#))
2. History of severe or life-threatening episode of anaphylaxis or anaphylactic shock within 60 days of Screening DBPCFC
3. History of chronic disease (other than asthma, atopic dermatitis, or allergic rhinitis) that is, or is at significant risk of, becoming unstable or requiring a change in chronic therapeutic regimen including autoimmune diseases and malignancies (including malignancies occurring in the 5 years prior to Screening)
4. History of EoE, other eosinophilic GI disease, chronic, recurrent, or severe gastroesophageal reflux disease (GERD), symptoms of dysphagia (eg, difficulty swallowing, food “getting stuck”), or recurrent GI symptoms of undiagnosed etiology
5. Current participation in any other interventional study and/or participation in another interventional clinical study within 30 days or 5 half-lives of the IP, whichever is longer, prior to randomization
6. Participation in, and having received active treatment in, any previous clinical study of AR101 CODIT
7. Currently receiving, or having received in the 5 years prior to Screening, any type of peanut or any other food immunotherapy clinical study (including subcutaneous, sublingual, oral, or epicutaneous)
8. Subject is in “build-up phase” of immunotherapy to another allergen (ie, has not reached maintenance dosing)
9. Severe asthma (2007 NHLBI Criteria Steps 5 or 6, [Appendix 2](#))
10. Mild or moderate asthma (2007 NHLBI Criteria Steps 1 to 4), if uncontrolled or difficult to control as defined by any of the following:

- Forced expiratory volume in 1 second (FEV₁) < 80% of predicted, with or without controller medications (only for age 6 years or greater and able to do spirometry¹); *or*
- Inhaled corticosteroids (ICS) dosing of > 500 mcg daily fluticasone (or equivalent ICS based on NHLBI dosing chart); *or*
- 1 hospitalization in the past year prior to Screening for asthma; *or*
- Emergency room (ER) visit for asthma within 6 months prior to Screening

11. History of high-dose corticosteroid use (eg, 1 to 2 mg/kg of prednisone or the equivalent for > 3 days) orally or parenterally in any of the following manners:

- History of daily oral or parenteral corticosteroid dosing for > 1 month during the past year; *or*
- 1 oral or parenteral corticosteroid course in the past 3 months; *or*
- > 2 oral or parenteral corticosteroid courses in the past year ≥ 1 week in duration

12. Inability to discontinue antihistamines 5 half-lives before the initial day of escalation, SPT, or Screening DBPCFC

13. Lack of an available palatable vehicle food to which the subject is not allergic

14. Use of any therapeutic antibody (eg, omalizumab, mepolizumab, reslizumab, dupilumab, etc.), or any other immunomodulatory therapy excluding aeroallergen or venom immunotherapy, or corticosteroids within the past 6 months ([Section 5.10](#))

15. Use of beta blockers (oral), angiotensin-converting enzyme (ACE) inhibitors, angiotensin-receptor blockers (ARB), calcium channel blockers, or tricyclic antidepressants ([Section 5.10](#))

16. Pregnancy or lactation

17. Residing at the same address as another subject in this or any peanut OIT study

18. Developing DLS in reaction to the placebo part of the Screening DBPCFC

19. History of a mast cell disorder, including mastocytosis, urticaria pigmentosa, and hereditary or idiopathic angioedema, and chronic spontaneous urticaria or other physician-diagnosed physical urticaria syndrome

20. Allergy to oat

21. Hypersensitivity to epinephrine or any of the excipients in the IP

¹ Spirometry is to be attempted in all subjects ≥ 6 years of age. For subjects 6 to 11 years of age: if valid spirometry results are not successfully obtained, the attempt is to be documented. Measures of peak flow will be acceptable for the entry criteria if results are > 80% of predicted. For subjects 4 or 5 years of age, peak flow rates are to be attempted, but reliable performance is not required for the subject to enter the study or undergo study procedures at the investigating physician's discretion. The attempt must be documented, and a clinical assessment is required.

22. Any other condition that, in the opinion of the investigator, precludes participation for reasons of safety
23. Inability to follow the protocol requirements
24. Patients being in any relationship or dependency with the sponsor and/or investigator
25. Subjects with a history of alcohol, medication or drug abuse

